### e) LPS administration induces robust microglial activation, anhedonic symptoms, and neurocognitive

[figure not shown]

Figure 6. Percent change in LPS-induced ROPER28X, values global and values global an

*dysfunction in healthy adults*. After initial studies in baboons(100), we assessed the neuroinflammatory response produced by systemic administration of the *E. coli* lipopolysaccharide (LPS; also called endotoxin) in 8 healthy men (mean age=25, SD=5.5) using [C]PBR28 and PET(13). In addition, peripheral cytokine levels and depression-related symptoms were assessed before and after LPS administration. Each subject had two [C]PBR28 PET scans in one day, one before and one 3 h after an LPS (1.0 ng/kg, IV) challenge. **LPS** administration significantly increased [C]PBR28 *V*T by 30-60%, demonstrating robust microglial activation throughout the brain (Figures 5 and 6). Notably, the increase occurred in all 8 subjects. This increase was accompanied by an increase in peripheral inflammatory cytokines, vital sign changes, mood symptoms(13) and a significant reduction in learning and memory performance (r= -0.60, p=0.032). These data provide the first demonstration in humans that a systemic LPS challenge induces robust increases in microglial activation in the brain, with concomitant increases in peripheral inflammation, and anhedonic and neurocognitive symptoms. In Aim 2, we will use this established and robust paradigm to evaluate the role of LPS-induced increases in levels of activated microglia in the etiology of PTSD symptomatology.

4. Research Plan: Summarize the study design and research procedures using non-technical language that can be readily understood by someone outside the discipline. Be sure to distinguish between standard of care vs. research procedures when applicable, and include any flowcharts of visits specifying their individual times and lengths. Describe the setting in which the research will take place.

**Aim 1,** we will recruit 40 trauma-exposed individuals and 40 individuals with PTSD to participate in one [C]PBR28 PET scan and one structural MRI scan, which is necessary for PET data analysis. Measures of PTSD and related symptoms, measures of threat and loss symptoms, and neurocognitive function will be assessed before PET scan.

**Aim 2**, the same subjects from Aim 1 will undergo a second [C]PBR28 PET scan on the same day, 3 hours after LPS administration (1.0 ng/kg, IV). This will allow us to measure LPS-induced changes in microglial activation. The order of the scans is not randomized because it is preferable to obtain both carbon-11 scans (20-min half-life) on the same day to reduce variability; and, because LPS likely has a relatively long-lasting effect on microglial activation/TSPO availability, it cannot be given prior to the first scan without affecting a second scan on the same day. Measures of PTSD and related symptoms, measures of threat and loss symptoms, and neurocognitive function will be assessed before and after LPS administration on scan days (timing of tests is detailed below) to determine whether inducing a systemic immune response dynamically affects these measures differentially between individuals with PTSD vs. trauma-exposed controls.

Aim 3, blood samples will be obtained on all subjects participating in Aims 1,2, and 5 before and after LPS

Page 8 of 45

administration on scan day to determine the relationship between peripheral cytokine levels, neuroinflammation, and dependent variables.

**Aim 4**, A) In order to define the relationship between neuronal and vascular inflammation we will recruit 40 subjects with PTSD and 40 trauma-exposed controls to participate in one whole body [F]FDG scan. Performing a "whole body" scan, i.e., brain to torso, allows us to measure brain and vascular/arterial inflammation in the same scan. B) These subjects will also have the option of participating in a whole body [C]PBR28 scan (on the same or different day).

**Aim 5**, the same subjects from Aims 1 & 2 will have the opportunity to undergo a third and fourth [C]PBR28 PET scan on subsequent days following LPS administration (these additional scans are optional and are not required for study participation). These additional scans will allow us to measure the approximate time course of neuroimmune recovery following LPS challenge in control and PTSD subjects. Subjects will complete both scans within one month following LPS administration. Measures of PTSD and related symptoms, measures of threat and loss symptoms, and neurocognitive function will be assessed immediately prior to each PET scan.

All subjects participating in PET scans will also have an MRI, which is necessary to rule out any brain abnormalities and for use in the PET image analysis. The MRI scan for an individual subject may be omitted if the required anatomical MRI scan for this subject is on file as part of participation in an approved Yale Protocol and was performed within approximately 6 months prior to the planned scanning time in this study.

Subject Selection, Assessment and Recruitment: All research subjects will be recruited in accordance with the guidelines of the Yale University Institutional Review Board (Human Investigation Committee). Subjects (n=160) will be recruited from the community via IRB-approved advertising (newspaper, radio, internet posting, television, flyers) and by referral from Yale outpatient psychiatric clinics. Over the past 10 years, we have successfully recruited individuals with psychiatric disorders, including PTSD(106), major depression(107), bipolar depression(108), alcohol dependence(109), and schizophrenia(110, 111), as well as healthy control subjects from the community for neuroimaging studies. After completing informed consent, subjects will undergo a physical and neurological examination, and an electrocardiogram (EKG). Laboratory tests will be performed to exclude subjects with medical complications and will include a complete blood count (CBC) and differential, chemistries, kidney function tests, liver function tests, and thyroid stimulating hormone tests. Subjects will be excluded for major medical, neurological or psychiatric illness (except PTSD and MDD, see below for details), abnormal laboratory tests, or contraindication to radiotracer or MRI. A urine drug screen and pregnancy test will be performed at screening and prior to both the PET and MRI imaging session, and subjects who screen positive will be excluded (except for cannabis). Trained, experienced research assistants under the direct supervision of Drs. [name] and [name] (both are licensed clinical psychologists) will initially evaluate subjects and administer the Structured Clinical Interview for DSM-5 (SCID-5) to ascertain psychiatric status, and the CAPS-5 to assess severity of PTSD symptoms and determine eligibility for participation. Physical and neurological examinations including a detailed history will be performed or overseen by a study physician who will review all of the clinical information, including laboratory results, and in collaboration with Drs. [name] and [name], will determine eligibility of study subjects.

Page 9 of 45

#### **PET Scans**

PET scans will be performed at the Yale University PET Center. An antecubital venous catheter will be used for IV administration of the radiotracer and for venous blood sampling. A radial artery catheter will be inserted by an experienced health care provider (an experienced physician or a highly skilled APRN trained to complete this procedure) in the morning before the PBR28 PET scan (FDG does not require arterial sampling). The site will be anesthetized with lidocaine prior to arterial line insertion. The arterial line will remain in place for the whole day of scanning, after which it will be removed. The IV catheter will also remain in place for the duration of the scan day. For Aims 1,2 and 5, PET scans are acquired as subjects rest using either an HRRT (207 slices, resolution better than 3 mm FWHM in 3D acquisition mode), HR+ PET scanner, or a Siemens mCT PET scanner (resolution better than 5 mm FWHM). A transmission scan, or low dose CT scan, will be obtained for each emission scan. Up to a total of 4 low-dose CT scans may be completed for the entire study. A transmission scan is obtained before each emission scan. On the HRRT PET scanner, motion correction will be performed dynamically with measurements from the Vicra (NDI Systems, Waterloo, Ontario) using a dedicated list-mode reconstruction algorithm 74. A dynamic PET scan of up to 2 hours duration will be acquired after IV bolus or bolus plus infusion of up to 18mCi of [C]PBR28. For Aim 4, subjects will be administered up to 10 mCi of FDG and may also be administered up to 20mCi of [11C]PBR28 to be scanned on the Siemens mCT PET/CT scanner (this is the whole body scanner) which includes CT attenuation scans. For the FDG PET scans, subjects are asked to follow a low carbohydrate diet for 24 hours prior to the scan and to fast overnight the night before. For FDG scans, FDG will be administered (up to 10 mCl, IV), and subjects rest for up to 2 hours prior to the 2 hr scanning period. The 2 hr rest period is necessary for the FDG uptake to occur. The PBR28 scans occur immediately following injection.

Vital signs may be taken immediately prior to injection of radiotracer, immediately after injection, at approximately 120 minutes after injection, and at the end of the last emission scan. Any adverse events will be evaluated and recorded continuously through the PET imaging day.

When arterial cannulation has been performed by a qualified health care provider, in the first phase of the scan (5-10 min), the arterial input functions are measured with an automated blood counting system (PBS-101, Veenstra Instruments, Joure, The Netherlands) using a continuous withdrawal system where the radioactivity in whole blood is measured with a calibrated radioactivity monitor. Subsequently, individual blood samples (venous and / or arterial) are taken at various time points and counted in a gamma counter. Samples are centrifuged to obtain plasma, which will be counted, and selected samples will be assayed for the presence of the parent radiotracer compound that has not been metabolized. These measurements will be performed by HPLC. In addition, the fraction of plasma radioactivity unbound to protein will also be determined.

#### **Endotoxin administration**

Subjects will receive intravenous administration of open-label endotoxin at a dose 0.8 - 1ng/kg body weight. This will take place at the Yale PET Center. All subjects will fast for at least 8 hours before endotoxin administration to reduce the risk of nausea, but they will be encouraged to hydrate well. They will be asked not to use aspirin, NSAIDs, COX-2 inhibitors, or acetaminophen for at least 3 days prior to each study day. Clinical Center Reference Endotoxin (CCRE) will be produced by List Labs and will be stored and prepared by the YNHH IDS pharmacy. CCRE is an investigational drug, and investigator [name] has obtained an Investigational New Drug (IND) for its use in humans from the Food and Drug Administration (FDA). CCRE vials will be stored at 2-8°C in a refrigerator in the locked YNHH IDS pharmacy. Preparation of CCRE will be performed by the YNHH IDS research pharmacist. As recommended by NIH, the pharmacist will dissolve the lyophilized CCRE in Sterile Water for Injection USP under a laminar flow hood on the evening before each endotoxin administration. The dissolved CCRE will be stored at 4°C until the following morning.

Dissolved CCRE is stable for at least 24 hours at this temperature.

On the day of endotoxin administration, subjects will rest on a stretcher in the PET Center. A urine drug screen

# Page 10 of 45

and breathalyzer will be done, as will a urine pregnancy test for women. An IV catheter will be placed to allow for hydration with normal saline, endotoxin infusion, and blood draws. In the case of bradycardia or hypotension, this catheter will be used for rapid bolus infusion of normal saline (van Eijk, Pickkers et al. 2004). To reduce the already low risk of adverse cardiovascular events, subjects will be hydrated with 500 mL of saline prior to endotoxin administration, and they will receive approximately 100 mL/hr thereafter for the duration of the endotoxin administration day.

After endotoxin administration, vital signs (blood pressure, heart rate and temperature) will be recorded every 15 minutes for the first two hours. If vital signs change significantly, monitoring will continue at least every 30 minutes, or more frequently as determined by the study MD, until they have returned to within 10% of the baseline values. All subjects will be connected to continuous two-lead EKG monitoring for the duration of the challenge. All subjects will be carefully monitored at all times by a research nurse and by a study physician or APRN (APRNs are trained on the protocol and will have MD telephone back up), who will be present until 3 hours after endotoxin administration. Any subject experiencing prolonged effects of endotoxin or any other adverse event may be transferred to the Yale New Haven Hospital emergency room if appropriate.

There is no evidence that experimental endotoxin administration causes hypoxemia in humans and therefore there is no literature to support monitoring of this parameter (as opposed to parameters such as heart rate and blood pressure, which do change and thus, will be monitored closely). Furthermore, pulse oximetry can be unreliable when there is significant peripheral vasoconstriction, as occurs during e.g. experimental endotoxemia, sympathetic activation, and fever.

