
6. Pregnancy and Breast Feeding: Since the acceptable levels of radioactivity are lower for pregnant individuals, women will be excluded from participating in this study if they are currently pregnant or might become pregnant during the study. They will be tested for pregnancy as part of the routine laboratory tests. If the test is positive, they will not be included in the study. Before starting the study, we will ask women to avoid becoming pregnant and what precautions they plan to take. We ask women to tell us immediately if they change their minds about becoming pregnant. If the woman is currently breast-feeding, she will be excluded from the study. Women will be given one pregnancy test during the initial physical evaluation, and in addition on day of the MRI scan and PET scans, prior to radiotracer injection.

7. Lipopolysaccharide Administration: Lipopolysaccharide (LPS, also called endotoxin) is a large molecule found on the outer membrane of gram-negative bacteria that has been widely used to evoke a robust immune response. We propose to use the same dose and protocol of LPS that we have successfully used in our recent study(13): 1.0 ng/kg, IV bolus. Specifically, on the day of the [C]PBR28 PET scans, LPS (0.8-1.0 ng/kg, IV) will be administered 3 hours prior to the second PET scan. Vital signs (systolic and diastolic blood pressure, heart rate and respiration rate) and sickness and psychiatric symptoms will be monitored before drug administration and every 15 minutes for the first two hours. If vital signs change significantly, monitoring will continue at least every 30 minutes, or more frequently as determined by the study MD, until they have returned to within 10% of the baseline values. Because of the risk of nausea and emesis, subjects are required to fast for the day of the study until after the scan. In our experience to date, no subjects have reported nausea that was significant enough to require stopping the study. If significant nausea or other adverse events occur, the study will be stopped.

Page 19 of 45

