If an individual experiences bothersome symptoms after LPS administration and wants to stop the study, flu-like symptoms may be treated with acetaminophen (650 mg every 6 hrs), or ibuprofen (400 mg every 6 hrs), and anxiety may be treated with lorazepam (0.5 mg every 2 hrs for a maximum dose of 6 mg every 24 hrs). During screening each subject will be asked about medication allergies, and no medication to which a subject may be allergic will be administered. If a subject requests, the study will be stopped and these medications may be administered. If a subject's body temperature exceeds 39.2°C the study will be halted and the subject will receive ibuprofen or acetaminophen as described above. If these medications are insufficient to lower body temperature, subjects may be transferred to a higher level of care.

At the end of the PET scan day, subjects will be assessed (physical and vital signs) by the study physician. Subjects will be discharged when vital signs are within normal limits and when behavioral changes (if any) are found to be not clinically significant by the MD attending to the subject at the PET Center. If subjects experience any adverse events, they will be treated until they become asymptomatic, prior to discharge. In the proposed study and in our ongoing studies, psychiatric patients who are administered a challenge drug may be admitted to an inpatient unit if psychiatric symptoms worsen or become dangerous on the PET scan day. Arrangements for a guaranteed bed will be made in advance of each PET scan day with the Clinical Neuroscience Research Unit (CNRU), located at the Community Mental Health Center (CMHC), which is 1 block from the Yale PET center. To date, no psychiatric patient has required admission. All subjects are followed for 1 week (in person the following day and by phone thereafter) following LPS administration or until potential symptoms (self-report and by assessment) resolve.

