A review of the literature published in 2007(123) describes all the studies wherein LPS was given to human subjects. All articles were reviewed for any potential adverse effects, morbidity or mortality; however, no long-term morbidity or mortality was reported in these more than 1000 healthy volunteers. At a 5 ng/kg dose of EC-5, subjects experienced nausea, vomiting and fever. Consequently, doses of  $\leq$  4 ng/kg have been subsequently used. We are giving 1/4 of that dose. LPS given at 2 ng/mg is not associated with known long-term sequelae or serious adverse events in healthy populations. Subjects (up to 4 total) who did have side effects at doses as low as 2 ng/kg were found to have underlying medical issues. When side effects have occurred, they are remarkably similar. Typically, within 50-90 min following LPS, subjects describe flu-like symptoms such as fatigue, malaise, arthralgias, myalgias, headache, nausea, and often chills that resolve within 3-4 h. Fever, however, is the hallmark of LPS infusion. After a latent period up to 120 min, there is a monophasic increase in fever which peaks at 1-2°C above baseline. The fever may last up to 3-4 h (depending on dose) and resolves without residual effect.

Page 20 of 45

This critical review of all the cases of LPS administration in human subjects concludes as follows, "for well over a century, endotoxin has been intentionally administered to humans for therapeutic purposes, for the evaluation of anti-inflammatory reagents as well as to address basic scientific questions of endotoxin biology. Much has been learned from the use of this model, and it has proved to be remarkably safe. Well over 1,000 subjects have been studied, yet we were able to find documentation of only five serious adverse events, and these were in subjects who were later shown to have vagal hypersensitivity,"(123).Thus, all the available data support that LPS administration in healthy human subjects is safe.

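### After LPS, the 10% rule for ending extended vital-sign readings does not work for temperature, and a subject unchanged at 2 h has no required temperature until the end-of-day check

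*Combined protocol and SAP*

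**What the plan says.** **Schedule after LPS.** Section I, item 4, Endotoxin administration, names blood pressure, heart rate and temperature. These "will be recorded every 15 minutes for the first two hours. If vital signs change significantly, monitoring will continue at least every 30 minutes". The study physician can shorten that interval, and the extended readings run "until they have returned to within 10% of the baseline values". A significant change is not defined, and the 10% applies to all three signs alike.

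**Second statement of the schedule.** Item 10, Risks, Lipopolysaccharide Administration, repeats the 15-minute, 30-minute and 10% rules, but its list omits temperature: "Vital signs (systolic and diastolic blood pressure, heart rate and respiration rate) and sickness and psychiatric symptoms will be monitored".

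**Around the scan.** LPS "will be administered 3 hours prior to the second PET scan", and "A dynamic PET scan of up to 2 hours duration will be acquired". Under PET Scans, "Vital signs may be taken immediately prior to injection of radiotracer, immediately after injection, at approximately 120 minutes after injection", and again when the last emission scan ends. These readings are optional and temperature is not named.

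**End of day.** "At the end of the PET scan day, subjects will be assessed (physical and vital signs) by the study physician". Discharge then requires vital signs in the normal range.

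**Expected fever.** The side-effects text in item 10 says: "After a latent period up to 120 min, there is a monophasic increase in fever which peaks at 1-2°C above baseline". It gives a duration of up to 3-4 h, depending on dose.

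**Where temperature is used.** A subject is halted above 39.2°C. The vital-signs grading table in item 12 starts Grade 1 fever at 38.0°C, sets Grade 3 at 39.0-40°C and Grade 4 above 40°C. The Study Stopping Criteria (more than 2) and the Study Hold Criteria (2 or more) count Grade 3 events related to endotoxin.

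**The concern.** Two weaknesses affect the same measurement.

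The first is the rule for ending extended readings. A percentage band can suit heart rate or blood pressure, where 10% is a modest departure. Body temperature moves by only a few percent between normal and dangerous, so a 10% band covers almost the whole febrile range. This does not depend on late onset. A subject already febrile at 2 h also meets the temperature part of the rule.

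The second is coverage after 2 h. If nothing has changed significantly by then, no text requires a temperature until the end-of-day check. By the plan's own description, a late fever could rise and peak in that interval.

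The 39.2°C halt and the fever grades work only if someone takes a temperature. Without a reading the halt may come late or not at all, and a Grade 3 fever may be recorded at a lower grade. Because the hold and stopping rules turn on two and three Grade 3 events, one misgraded fever could change a decision.

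**Working it through.** The plan states no figure to reproduce on this point. It gives no baseline temperature, so the baselines below are assumptions.

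**1. Upper edge of the 10% band: 1.10 x baseline**

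| Assumed baseline (°C) | Upper edge (°C) | Against 39.2°C halt | Against Grade 4 (above 40°C) |
|---|---|---|---|
| 36.0 | 39.60 | above | below |
| 36.5 | 40.15 | above | above |
| 37.0 | 40.70 | above | above |
| 37.5 | 41.25 | above | above |

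Break-even baselines: 39.2/1.10 = 35.6°C for the halt and 40/1.10 = 36.4°C for the top of Grade 3. For any baseline above 35.6°C, a subject at the halt temperature already counts as returned. From 37.0°C, the expected 1-2°C rise is 1/37.0 = 2.7% to 2/37.0 = 5.4%, and 39.2°C is 2.2/37.0 = 5.9%. A percentage of temperature also depends on the scale: 37.0°C is 98.6°F, and 1.10 x 98.6 = 108.5°F, or 42.5°C, against 40.7°C when computed in Celsius.

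**2. The interval without a required temperature**

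- Fixed readings: 120/15 = 8, the last at 2 h.
- Second scan: starts at 3 h and lasts up to 2 h, so it ends by about 5 h.
- Longest interval for a subject unchanged at 2 h: 5 - 2 = about 3 h, and less if the scan is shorter.
- Fever starting at 2 h and lasting 3-4 h: runs from 2 h to 5-6 h, so it overlaps the interval.

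**3. Who could reach the thresholds**

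- Grade 3 with the full 2°C rise needs a baseline of at least 39.0 - 2.0 = 37.0°C.
- The halt needs a baseline above 39.2 - 2.0 = 37.2°C.
- A 1°C rise from 37.5°C gives 38.5°C, which is Grade 2.

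**4. Worst-case illustration**

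Assumed: baseline 37.5°C, rise 2.0°C, onset at 2 h, straight-line rise and equal fall. The true peak is 39.5°C, which is Grade 3 and above the halt.

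| Duration | 3 h | 3.5 h | 4 h | 5 h |
|---|---|---|---|---|
| 3 h (peak at 3.5 h) | 37.5 + 2.0 x 1/1.5 = 38.8 | 39.5 | 38.8 | 37.5 |
| 4 h (peak at 4 h) | 37.5 + 2.0 x 1/2 = 38.5 | 37.5 + 2.0 x 1.5/2 = 39.0 | 39.5 | 38.5 |

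An end-of-day reading at 5 h alone shows no graded fever in the first row and Grade 2 in the second. Readings at 3, 4 and 5 h catch the second peak but miss the first: 38.8, 38.8 and 37.5°C are all below 39.0°C. The first peak is caught only if the 3 h value starts 30-minute readings, which would include 3.5 h.

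**The case against.** The case against has several good parts.

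- **Subjects are watched.** PET Scans requires adverse events to be evaluated and recorded throughout the imaging day. Endotoxin administration adds continuous EKG and nurse monitoring, and stops a subject for symptoms that prevent normal activity. A symptom checklist and blood draws about every 30 minutes add contact. This stands, and it rules out the inference that subjects go unobserved for 3 h. None of these provisions requires a temperature.
- **Discharge is protected.** A reader might infer that a febrile subject could be sent home under the 10% rule. The documents do not support that: the discharge rule in item 10 asks for normal vital signs, which works for temperature. The flaw is confined to ending extended readings.
- **The other signs help.** Readings continue until the vital signs as a group have returned, and item 10 lists raised heart rate beside fever. A fast heart rate would often keep temperature readings going. The flaw therefore matters only when blood pressure and heart rate have settled first. Nor is it true that temperature can never hold readings open: from 36.5°C, anything above 40.15°C would.
- **A clinician would not apply 10% literally to a fever.** Probably so, but the rule should not rely on being disregarded.
- **The late case is uncommon.** It needs no significant change over eight readings, then late onset. Item 10 puts the peak of effects near 90 minutes. Its account draws on doses of 2 ng/kg and above, against 0.8-1.0 ng/kg here. This stands.

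**Conclusion.** Both parts hold, at minor severity.

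The return rule is wrong as written for temperature. That follows from arithmetic for any baseline above 35.6°C. The statement that the band also passes the Grade 4 boundary needs a baseline above 36.4°C.

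The interval without a required temperature is also real on the text, but narrower in effect. It applies to subjects with no significant change by 2 h, and 5 h is its outer limit because it assumes a full-length scan. How many subjects would have a fever peak inside it cannot be estimated: the documents give no fever rate or timing at 0.8-1.0 ng/kg. The 39.5°C illustration rests on assumed baseline, rise, onset and shape, and it is a worst case.

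A reader might infer that severe fevers have been missed, or that an aim or endpoint is compromised. The documents support neither. The sponsor reports more than 30 subjects at this dose without unexpected or serious effects, and no planned analysis uses the fever readings. What is at stake is whether the plan's own halt and fever grades can work as intended.

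**What to change.** 1. In Endotoxin administration and in item 10, keep 10% for blood pressure and heart rate. Give temperature an absolute return limit set by the study physician, for example below 38.0°C, the lower edge of Grade 1.
2. State that any reading of 38.0°C or more counts as a significant change and starts the 30-minute readings. This is needed because hourly readings alone can miss a short peak.
3. For the post-LPS scan, make the vital signs under PET Scans mandatory and name temperature.
4. Add a temperature at the 4 h draw already required under Inflammatory cytokines, so that readings fall at about 3, 4 and 5 h.
5. Add temperature to the vital-sign list in item 10.
6. The grading table assumes oral temperature, so record the site if another method is used.

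**Cost.** A short amendment and a revised scan-day worksheet. One temperature at each of three time points is 3 x 80 = 240 readings over the 80 LPS subjects. Taking one at all four times listed under PET Scans plus 4 h would be 5 x 80 = 400. Triggered 30-minute readings would add to either figure. Nursing staff are already promised during scans under item 11, and blood is already drawn at 3 h and 4 h. The practical drawback is that readings during the scan need a method that does not move the head.
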